## 28.0 Data and Specimen Management\*

9.

1. **Data Management:** *Describe how data will be handled, including:*

- *What information will be included with the data?*

- *Intervention Trial Participants:* Survey information included as data will be questions from our eligibility screen, baseline survey, Event Day Survey Measures(optional) and 2-, 4-, and 6-month follow-up. We will ask adolescents about their health behaviors as well as some demographics to describe the group (age, gender identity, race). Attendance at study-related events, training, and group sessions will be included as data.
- *Event day Participants:* Survey information included as data will be questions from our eligibility screen, and Event Day Survey Measures (optional). For those receiving Clinical Care

the information included as data: Participation in Pregnancy test, STI testing for gonorrhea/chlamydia (urine), and STI testing for HIV and Syphilis (blood). Results for the following: pregnancy test, STI test results for gonorrhea/chlamydia/HIV/syphilis (urine and blood). Record of if birth control was received and which type. Record if referral to Children's Mercy Hospital Adolescent or Teen Clinic was given. All services are optional to teens.

- *How the data will be collected and stored. (e.g., REDCap, Excel, paper forms)*
  - All data will be directly accessible and stored securely via REDCap at CMKC.
- *How long will the data be stored?*
  - Contact information for teens that would like to participate in future research will be kept for 5 years and then destroyed. For teens that do not want to participate in future research, we will destroy contact information as soon as the study is completed. De-identified data will be stored in accordance with CMRI guidelines and will be deleted once IRB project is closed
- *Who will have access to the data?*
  - CM study team, students from the University of Kansas Medical Center (KUMC) and University of Missouri – Kansas City (UMKC) will have access. A reliance will be obtained from both institutions.
- *Who is responsible for receipt or transmission of the data?*
  - Trained CM research team members and students from the University of Kansas Medical Center (KUMC) and University of Missouri – Kansas City (UMKC)
- *Methods for transferring data.*
  - All data that is shared will be de-identified using a secure data transfer system.

## **2. Specimen Management:**

N/A

## **3. Biosafety Information**

Will this study involve handling, transporting, or shipping any potentially hazardous biological material at/from a Children's Mercy location (e.g., blood, stool, saliva, tissue)?

Yes

No

Will this study involve processing any potentially hazardous biological material at a Children's Mercy location (e.g., blood, stool, saliva, tissue)?

Yes

No

If processing potentially hazardous biological materials, where will this work be conducted?

Pediatric Clinical Research Unit (PCRU)

Children's Mercy Research Institute labs (mySafety ID#: \_\_\_\_\_)

Other location

If "Other location," identify the location and mySafety ID# of the corresponding IBC protocol:

Location: \_\_\_\_\_

mySafety ID#: \_\_\_\_\_

## 29.0 Storage/Banking of Data and Specimens for Future Research

N/A

10.

## 30.0 Provisions to Monitor the Data to Ensure the Safety of Subjects

*This section is required when research involves more than Minimal Risk to participants.*

N/A: Our study involves no more than minimal risk to participants

11.

## STUDY MANAGEMENT

### 31.0 Setting & Locations\*

12.

- *Describe the sites or locations where the research will be conducted.*
- Research may be conducted in a variety of settings including the community, within CMRI, virtually on Microsoft TEAMS, as well as at mobile unit events at community partner locations.

*Identify where research procedures will be performed including any non-CM affiliated locations. For any non-CM affiliated locations, upload a letter of support in myIRB which states that the site is aware that research will be conducted on their premises.*

- Community Partners:
  - a) Mattie Rhodes Center

*[name]*

*[name]*

- b) *Front Porch Alliance*

*[name]*

*[name]*

*Describe the composition and involvement of any community advisory board.*

- For intervention refinement we will form a Community Action Board (CAB) to 1) refine proposed content, 2) generate strategies for outreach (e.g., social media), education (e.g., group sessions), and support to inform peer leader training, 3) guide toolkit development (described below), 4) confirm sites to host the MHU for care and telemedicine demonstrations, 5) inform outcome measures. We will meet (virtually/in-person) biweekly then monthly (or as needed) during implementation. The CAB will be composed of key stakeholders from the community including about 10 adults and about 10 teens. The CAB participants are not engaged in research.
- *For research conducted outside of CM and its affiliates describe:*
  - *Regulations or customs affecting the research*
    - N/A
  - *The local scientific and ethical review structure*
    - N/A
  - *Describe the availability of medical or psychological resources that subjects might need as a result of taking part in the study.*

## 32.0 Multi-Site Research

13.

- 1. **Students:** Describe *any student involvement in the protocol (only when a reliance is necessary). Remove section or mark 'n/a' if students are not involved.*
- Student from KUMC will assist with recruitment, enrollment, and data collection through survey administration. They will also assist with data analysis and dissemination.
- 2. **Study-Wide Number of Subjects:** *If this is a multicenter study, indicate the total number of participants to be accrued across all sites. Additionally, list out the enrollment numbers planned for each site.*
- N/A

## 33.0 International Research

14.

- 1. *Describe any research conducted internationally by CM investigators that is part of this study. If research is conducted internationally, the project must also have been approved by the local equivalent of an IRB before it can receive final approval from the CM IRB. When there is no equivalent board or group, investigators must rely on local experts or community leaders to provide approval. Upload related correspondence in myIRB. Contact ORI at [[contact]](mailto:[contact])*

*to discuss further as there is a great deal of variation in requirements internationally and this assessment can take some time.*

- N/A

## **Addendum A: Waiver of Documentation of Permission/Consent**

**Regulatory Criteria:** *To qualify for a waiver of documentation of parental permission or adult consent, the study must fit into at least one of the three scenarios below. Indicate which scenario(s) applies.*

**The only record linking the participant and the research would be the permission/consent form and the principal risk is potential harm resulting from a breach of confidentiality.**  
Each parent/LAR or adult participant will be asked whether they want documentation linking the participant with the research, and the parent/LAR's or adult subject's wishes will govern.

OR

**The research presents no more than minimal risk of harm to participants and involves no procedures for which written parental permission or adult consent is normally required outside of the research context.**

OR

**The parent(s)/LAR or adult participants are members of a distinct cultural group or community in which signing forms is not the norm, the research presents no more than minimal risk of harm to subjects and an appropriate alternative mechanism for documenting that informed parental/LAR permission or adult consent was obtained will be provided.**  
Describe the alternative mechanism provided:

Addendum B: Waiver/Alteration of Permission/Assent/Consent: Waiver of parental permission of adolescent and Waiver of adult consent at age 18 (Non-Active Participants) Adolescent participants that turn 18 during the study and have completed study activities for the continued access to and use of identifiable data.

**What's the difference between a “waiver” and an “alteration” of parental permission, child assent, or adult consent?**

A “waiver” of parental permission, child assent, or adult consent is when **all 9 required elements of permission/consent are waived**. If the IRB approves a waiver, then the study team does not need to obtain the parental permission or adult consent in order to include a participant in the study.

An “alteration” of parental permission, child assent, or adult consent is when **one or more of the 9 required elements are waived** because they are not relevant to the research activity. If the IRB approves an alteration, then the study team must still obtain parental permission or adult consent in order to include a participant in the study, but certain elements may not be required in the form/discussion.

**NOTE:** If requesting a waiver of parental/LAR permission because parental permission is not a reasonable requirement to protect the subjects [e.g. research on neglected or abused children], contact [[contact]](mailto:[contact]) to discuss additional regulatory requirements.

**Regulatory Criteria:** *To qualify for a waiver or alteration of parental permission or adult consent, **ALL** of the following must apply. Explain how the study meets each of the regulatory criteria below.*

Criteria	Explain how the study meets the criteria
The research involves no more than minimal risk to the subjects	Adolescents will be completing confidential surveys. Risks are minimal and mitigated by the option to skip any question that they do not want to answer and by the confidentiality procedures we have in place to protect personal information.
The research could not practicably be carried out without the requested waiver/alteration (i.e., explain why the study could not be done if permission/assent/consent were required)	
Adolescents will be recruited virtually or in-person where parents may not be present. Also, some teens would not want to participate if we could not maintain privacy on the potentially sensitive research topics. Requiring parental permission would mean many teens interested and eligible would not be able to participate. This could lead to sample bias and inaccurate study findings and ultimately could cause harm to adolescents.
 
Additionally, assent was obtained utilizing the Information Sheet. Continued access to and use of identifiable data is needed to meet the study aims for participants that turn 18 during the study and have completed study activities.

If the research involves using identifiable private information or identifiable biospecimens, the research could not practicably be carried out without using such information or biospecimens in an identifiable format	
Because of the 2, 4, 6-month follow-up survey, we will need to collect at least one form of contact information (phone number, email).
 
Additionally, continued access to and use of identifiable data is needed to meet the study aims for participants that turn 18 during the study and have completed study activities.

The waiver/alteration will not adversely affect the rights and welfare of the subjects	
We have no reason to believe that this waiver will adversely affect the rights of participants. On the contrary, we believe it will protect their rights, as teens may be more comfortable participating in a study about sexual and mental health without the involvement of their parents.
 
The Waiver will not adversely affect the rights of non-active participants that turn 18 during the study as assent was obtained utilizing the Information Sheet.


Whenever appropriate, the subjects or legally authorized representatives will be provided with additional pertinent information after participation
	
Because our participants are older minors (14 and up) we are including in the assent everything that would be typically included in an adult consent form. We believe not providing study information to parents participating in a study about their sexual and mental health, may protect teen rights and privacy without the involvement of their parents. They may choose to share their decision with parents and trusted adults.
 
Whenever appropriate, the subjects or legally authorized representatives will be provided with additional pertinent information after participation

--	--

**Proposed Alteration (if applicable):**

N/A

***Addendum E: Waiver/Alteration of HIPAA Authorization***

**What's the difference between a “waiver” and an “alteration” of HIPAA Authorization?**

A “waiver” of HIPAA Authorization is when **the requirement to obtain authorization is completely waived**. If the IRB approves a waiver then the study team does not need to obtain HIPAA Authorization in order to include a subject in the study.

An “alteration” of HIPAA Authorization is when **one or more of the required elements of authorization are waived**. If the IRB approves an alteration then the study team must still obtain HIPAA Authorization in order to include a subject in the study, but certain elements may not be required in the form/discussion.

**Regulatory Criteria:** *To qualify for a waiver/alteration of HIPAA Authorization, **ALL** of the following must apply to a study. Explain how the study meets each of the regulatory criteria below.*

Criteria	Explain how the study meets the criteria

The use or disclosure of PHI involves no more than minimal risk to the privacy of individuals based upon the following:
 

○ Plan to protect PHI from improper use and disclosure:

○ Plan to destroy PHI at the earliest opportunity, unless there is a health or research justification for retaining the PHI:

○ Assurance that PHI will not be reused or disclosed to any other person or entity:

	
a. PHI will only be kept in the REDCap project, accessible only to authorized members of the study team
 
b. We will remove all PHI from the REDCap database after the last contact. Names and contacts of participants that indicate they would like to be contacted for future research will be stored in a separate secure database away from study materials.
 
c. PHI will not be reused or disclosed to any other person or entity

The research cannot practically be conducted	We have requested an alteration for HIPPA


without the waiver/alteration, i.e. explain why a signature for HIPAA Authorization cannot be obtained.
	
Authorization to reduce stress and anxiety that could potentially occur if adolescents are asked to provide signature for minimal risk study. Participants may choose not to participate which could affect the sample size and bias results for the research.
 
Some teens may have distrust in medical research based on a long history of abuse perpetrated against marginalized populations. In order to improve communication and reduce anxiety for this minimal risk study, we seek this alteration.

The research cannot practicably be conducted without access to and use of the PHI, i.e. explain why access to PHI is needed for this study.
	
Names, phone numbers and emails are needed in order to contact the survey participant for the follow-up surveys and to send educational messages to the peer leaders throughout the study.

Increasing Teen Access to Care (AccessKCTeen2)

NCT05444855

05 September 2023

Statistical analysis plan

We will use R software (R Foundation for Statistical Computing) for analyses. We will conduct descriptive analysis with inferential and graphical exploratory analytic techniques, presenting mean, median, and interquartile range [continuous variables] and frequency and percentage [categorical variables]. Next, bivariate analyses will be conducted to assess the relationship between variables. We will examine data for outliers and/or high leverage points and use established best practices in decided how to address them.

We will compare outcomes using independent t-tests for continuous variables and Chi-Square or Fisher's exact test for categorical variables depending on cell counts. If continuous variables are highly skewed nonparametric testing will be implemented (i.e., Wilcoxon rank-sum test). All tests will be two-sided, assessed with significance of $p<0.05$. We will evaluate these feasibility constructs:(acceptability, demand, implementation, practicality, integration, expansion, limited efficacy [see primary outcome]) using descriptive statistics. *Primary outcome:* We will calculate the proportion of adolescents with any health care utilization at 6 months.

Attrition: We will use established methods to minimize attrition (see "Recruitment and Retention") and plan to assess for our primary outcome every two months to keep participants engaged and minimize bias. Participants who are lost to follow-up after three attempts at 6 months will be excluded from the denominators for hypothesis testing. We will report on demographics of those lost to follow-up compared to those who completed the study.

Missing data: We plan to minimize missing data by engaging our CAB to pretest survey measures to achieve brevity and clarity. Our electronic data collection tool (REDCap) can be set to require participant responses before advancing. In order to identify potential problems promptly, we will run a REDCap report every second week to review the degree of missingness for each variable. Any variable missing $>5\%$ will be reviewed to determine probable causes and a plan will be developed to address the issue(s). During analysis, we will determine both the extent of missingness and whether data are missing at random (MAR). If the data are missing for $<20\%$ of responses, we will rely on list-wise deletion. If $\geq 20\%$ is missing we will utilize multiple imputation techniques. Specifically, we will determine if data are MAR by partitioning the data into two groups (those with and without missing data) and examining the distributions across variables of interest and employ appropriate imputation techniques.

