## STUDY INFORMATION

### 1.0 Study Summary\*

#### 1.1 Synopsis

Study Title	AccessKCTeen 2.0: Increasing teen access to care using peer social networks and mobile health services.
Study Design	Open Clinical Trial
Primary Objective	To evaluate our novel multi-level intervention to increase access to care called TeenHealth Outreach+ (THO+).
Secondary Objective(s)	N/A
Study Population	

Adolescent participants: clinical trial (intervention trial participants as friend network or peer leader) and/or event day participants

	Up to 250 adolescent participants, including up to 40 peer leaders.
Study Duration for Individual Participants	Up to 7 months for adolescent clinical trial participants, event participants complete single survey
Study Specific Abbreviations/ Definitions	(SRH) Sexual and Reproductive Health (MH) Mental Health (CM) Children's Mercy (MHU) Mobile Health Unit

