## **Study Design**

### **Study Design: Open Clinical Trial**

#### PROGRAM ACTIVITIES:

*AccessKCTeen 2.0* is an outreach program that deploys Children Mercy's Staff and Mobile Unit into the community to increase access to SRH and MH care and resources. *AccessKCTeen 2.0* will focus on education, peer leaders, and community partnership. All events are optional for adolescents to attend.

*Mobile Unit Demonstration Events:* The CM mobile unit will go to community sites where members of the CM *AccessKCTeen* team will do the following: provide education on telemedicine, SRH, and MH, answer questions on accessing care, SRH, and MH, and help adolescents get registered for telemedicine or other care at CM.

*Mobile Unit Clinical Care Events:* The CM mobile unit go to community sites where members of the CM *AccessKCTeen* team will provide direct clinical services, such as testing for infections or pregnancy, birth control counseling, and birth control.

Any teen can attend these events. If they choose to attend an event, they must enroll in our Event Day Survey, to receive clinical medications (e.g., emergency contraception, birth control pills, birth control patch) or testing as this is a requirement for pharmacy documentation. This survey will ask for contact information which is required to track clinical medications and provide testing results.

**THO+:** Teens as part of a friend network, where peer leaders in each network work with health professionals and trusted adults to connect adolescents in their networks to health information and sources for care.

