**Inclusion Criteria**

- Aged 14-18 years and 364 days old
  - a. **Exclusion Criteria**
- Younger than 14 years old or older than 18 years and 364 days at the time of enrollment
- Does not speak/understand English
- Not recruited from an already nominated or enrolled adolescent

*(2) Event Day Trail PARTICIPANTS (ADOLESCENTS)*

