**2. Equitable Selection:**

1. Adolescents within the social networks of enrolled adolescents will be selected for our sample population since peer networks heavily influence adolescents' health behavior choices. Peer networks that diffuse reliable information and positively influence norms have efficacy in connecting under-resourced adolescents to care.

**3. Vulnerable Populations:** *Check any vulnerable populations that are being targeted for enrollment into the study: (Members of the following populations may not be included as participants in the research unless selected here.)*

- Children/Minors (under 7 years of age)
- Children/Minors (7-17 years of age)
- Neonates (infants less than 30 days old)
- Neonates of Uncertain Viability (infants less than 30 days old)
- Non-Viable Neonates (infants less than 30 days old)
- Wards of the State
- Fetuses
- Pregnant Women
- Adults with impaired decision-making capacity
- CM Employees
- CM Students/Residents/ Fellows
- Economically or Educationally Disadvantaged Persons
- Prisoners

*Children/Minors (7-17 years of age):* Our research involves no more than minimal risk to children aged 7-17 years. To participate in this research study, adolescent participants must be between the ages of 14-18 years and 364 days of age. For adolescents this age, guidelines from national medical organizations support allowing for waiver of parental permission for minimal risk studies to support adolescent autonomy and since teens have the capacity to understand and consent for research studies. Adolescents will be provided as much time as they want to make their decision and can involve a trusted adult if they so choose. Further, state laws enable adolescents to have access to confidential SRH and MH care and to make decisions regarding their care. Because of this, we are requesting a waiver of parental permission to help maintain confidentiality around sensitive health care and to follow best practices to support adolescent autonomy.

*Economically or Educationally Disadvantaged Persons:* Our research is designed to address health disparities; thus, we involve communities experiencing these disparities such as those

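### Teens are recruited and served in friend networks, but no analysis accounts for this: an interval for 6-month utilization that treats teens as independent would be too narrow if outcomes correlate within networks

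*SAP*

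**What the plan says.** **Design.** The protocol's program description defines THO+ as "Teens as part of a friend network, where peer leaders in each network work with health professionals". Under section 8.0, first contacts come through community organizations or lists from the community action board. Enrolled teens then recruit from their own social networks, and the networks nominate a peer leader. One exclusion criterion for intervention participants in section 6.0 is "Not recruited from an already nominated or enrolled adolescent". The Equitable Selection paragraph justifies sampling through networks on the ground that "peer networks heavily influence adolescents' health behavior choices". Section 7.0 caps enrolment at 250 teens, of whom up to 40 are peer leaders.

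**Analysis.** The SAP's primary-outcome sentence reads "We will calculate the proportion of adolescents with any health care utilization at 6 months". It names no confidence interval, null value or threshold. For comparisons it says "We will compare outcomes using independent t-tests for continuous variables", adds chi-square or Fisher's exact tests for categorical variables and Wilcoxon rank-sum for skewed ones, and sets a two-sided 0.05 level. Teens lost at 6 months are "excluded from the denominators for hypothesis testing", so some inference is intended. Protocol section 27.0 plans logistic regression for utilization, with individual covariates such as sex and age and exploratory moderation by sex, age or engagement. Neither text mentions network, an ICC, a random effect, GEE or cluster-robust variance.

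**The concern.** Friends who recruit one another, share a peer leader and attend the same events are likely to resemble each other in whether they use care. The intervention's own rationale predicts this. Positive correlation means that 250 teens carry less information about the utilization rate than 250 independent teens would.

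The estimate is unaffected, but its precision is. A reader of a one-group feasibility result will want to know how closely the utilization rate is pinned down. An analyst following the methods named in the SAP would most naturally attach an ordinary binomial interval, which would be too narrow. The ICC and network sizes, which would help in planning a later network-based trial, would also go unreported.

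**Working it through.** **Inputs.** From the documents: at most 250 teens and at most 40 peer leaders (section 7.0), and a two-sided 0.05 level (SAP). Assumed, because the documents give no value: utilization 50%, ICC 0.01 to 0.20, one peer leader per network, and networks of equal size unless stated. The plan gives no sample-size calculation or interval width, so there is no figure of its own to reproduce.

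**Formulas.** With *n* teens in *k* networks and *m* = *n*/*k*:
- design effect DE = 1 + (*m* − 1) × ICC
- naive half-width = 1.96 × √(0.25/*n*)
- clustered half-width = naive half-width × √DE
- true coverage of the naive 95% interval = 2Φ(1.96/√DE) − 1

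**Lead case: 250 teens in 40 networks.** *m* = 250/40 = 6.25. The naive half-width is 1.96 × √(0.25/250) = 6.2 points. At ICC 0.10, DE = 1 + 5.25 × 0.10 = 1.525 and the half-width is 6.2 × √1.525 = 7.7.

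| ICC | DE | Effective n | Half-width (points) | Naive coverage |
|---|---|---|---|---|
| 0.01 | 1.05 | 238 | 6.4 | 94.4% |
| 0.05 | 1.26 | 198 | 7.0 | 91.9% |
| 0.10 | 1.53 | 164 | 7.7 | 88.8% |
| 0.20 | 2.05 | 122 | 8.9 | 82.9% |

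**Other sizes.** The synopsis describes the population as "clinical trial (intervention trial participants as friend network or peer leader) and/or event day participants", and event-day teens have no follow-up (section 11.0). Fewer than 250 may therefore be network members with a 6-month outcome. Over ICC 0.01 to 0.20:

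| Teens / networks | m | Naive half-width | Clustered half-width | Naive coverage |
|---|---|---|---|---|
| 200 / 40 | 5 | 6.9 | 7.1 to 9.3 | 94.5% to 85.6% |
| 150 / 40 | 3.75 | 8.0 | 8.1 to 10.0 | 94.7% to 88.5% |
| 100 / 40 | 2.5 | 9.8 | 9.9 to 11.2 | 94.8% to 91.4% |
| 250 / 20 | 12.5 | 6.2 | 6.5 to 11.3 | 93.7% to 71.9% |

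Unequal networks make it worse. With 40 networks of 2 to 16 teens (250 in all), simulated naive coverage falls from about 94% to about 77%.

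**Group comparisons.** This was simulated with the ordinary chi-square test at 5%, 250 teens in 40 near-equal networks, and outcome ICC 0.01 to 0.20. Type I error is about 5% when the grouping is unrelated to network. It reaches about 7.5% only when outcome ICC and grouping ICC are both 0.20. A contrast made within networks would be conservative.

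**Does a clustered interval work?** The robust variance is *k*/(*k* − 1) × Σ(*y*ⱼ − *n*ⱼ*p*)²/*n*², where *y*ⱼ is the number of users among the *n*ⱼ teens in network *j*, with t on *k* − 1 df. For 40 near-equal networks its simulated coverage is about 95% at every ICC tried; for the unequal networks it is about 94%. If the 40 recorded networks are really 20 linked pairs, coverage at ICC 0.20 is 87.4% unmerged and about 95% once the pairs are merged, with a half-width of 11.9 points.

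**Price if there is no clustering** (250 teens, mean half-width against 6.2): 6.4 with 40 clusters, 6.5 with 20, about 6.9 with 10 and about 8.2 with 5.

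**The case against.** The strongest reply is that no interval is planned. The SAP calculates a proportion and assigns the feasibility constructs to descriptive statistics; the hypothesis in section 2.0 is that teens will report the intervention as feasible, and no precision aim is stated. This stands, and it limits the point to an omission. A reader might infer that the primary result is wrong. It is not: correlation within networks does not make the planned calculation incorrect.

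A reader might also infer from "We will compare outcomes using independent t-tests for continuous variables" that the planned tests are invalid and should all be replaced by GEE or mixed models. The documents do not support that. The sentence concerns group comparisons, not the primary proportion. The groupings named in section 27.0 (sex, age, engagement) are not shown to follow network lines, and the inflation is mild even when they do. For attrition the SAP says only "We will report on demographics of those lost to follow-up compared to those who completed the study" and names no test for that comparison.

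The missing cluster term in the protocol's regression of intervention effect is likewise secondary. The THO arm was removed (Revision History, revision 3), so that contrast has no comparator. This is a separate issue.

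Finally, the size rests on assumptions: 250 and 40 are caps, and the ICC, rate and network sizes are unknown. That is why a range is shown, and at an ICC of 0.01 the effect is negligible.

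**Conclusion.** The concern holds as an omission. Network clustering is built into recruitment, eligibility and delivery, and neither plan provides a way to attach valid precision to the utilization proportion. If outcomes correlate positively within networks, an independence-based interval is too narrow. In the lead case the correct half-width is 3% (√1.05 = 1.03) to 43% (√2.05 = 1.43) larger over ICC 0.01 to 0.20. The effect is smaller with fewer teens per network and larger with fewer or unequal networks. For group comparisons it is minor. The direction follows from positive correlation alone; the size depends on assumed values. Priority is minor to moderate, since no stated decision rule uses the interval.

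**What to change.** - Keep a network ID and a recruiter ID for every intervention participant, and merge clearly linked recruitment chains into one cluster. The survey forms were not available for this review, so these fields may already exist. If not, they can be partly rebuilt from the payment and service-hour records in section 17.0, which cover recruitment by peer leaders only.
- Report the 6-month utilization proportion with a network-clustered 95% interval: cluster-robust variance with a small-sample correction and t on (networks − 1) df, or a whole-network bootstrap when there are enough networks.
- Report the number and sizes of networks after merging, and the ICC.
- Keep the planned group tests. Add a network-clustered sensitivity analysis for comparisons or regressions of utilization where the grouping tends to be shared within networks.

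**Cost.** One or two ID variables, a few sentences in the SAP and a little more analysis. If there is no clustering, the interval widens by about 0.2 points with 40 networks and 0.3 with 20, but by about 0.7 with 10 clusters and 2 with 5. Merging can leave few clusters, so their number should be stated beside the interval.
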